1.3. Schedule of Activities (SoA)

Table 1: Study Activities for Duvelisib Monotherapy (Cycle 1: 10 Weeks; Cycles ≥2: 4 Weeks)

Activity	Screening D-30 to D-1	Cycle 1					Cycle 2		Cycle 3+	EoT ^a	Safety F/U ^b 30d (+7) postdose		Notes
		D1	D14 (-3)	D29 (+3)	D43 (±3)	D57 (±3)	D1 (±3)	D14 (-3)					
Informed Consent	X												Potentially eligible subjects must sign an ICF prior to initiating any study specific procedures. Standard of care assessments that fulfill study eligibility requirements may be performed prior to subject signing the ICF.
Inclusion/Exclusion Criteria	X												
Randomization	X (D -7 to -1)												Subject must sign informed consent, meet inclusion/exclusion criteria, and complete all other screening activities prior to randomization.
Medical History, Demographics	X												Medical History includes histologic lymphoma diagnostic and prior treatment and response information, FLIPI-1 score
Archival Tumor Tissue	X												Tumor tissue is not required for enrollment, but should be submitted from all enrolled subjects, if available. Sample should be FFPE tissue and will be used to evaluate prognostic biomarkers.
Tumor Biopsy (optional)	X												If a transformation to a more aggressive subtype of lymphoma is suspected, a biopsy may be performed at Investigator's discretion. If this sample is collected, please see Archival Tumor Tissue instructions above.
Full Physical Examination	X	X											If performed within 7 days of C1D1, then screening results can be used for C1D1.
Focused Physical Examination			X	X	X	X	X	X	X	X			Disease-focused assessments including liver/spleen size, clinical assessment of tumor masses, and B symptoms.
Vital Signs	X	X	X	X	X	X	X	X	X	X			Vital signs measured in a semi-supine position after 5 minutes rest.
Computed Tomography (CT)	X									X			All subjects require CT or FDG-PET-CT scans. MRI may be used instead of CT scans if CT cannot

Activity	Screening D-30 to D-1	Cycle 1					Cycle 2		Cycle 3+	EoT ^a	Safety F/U ^b 30d (+7) postdose		Notes		
		D1	D14 (-3)	D29 (+3)	D43 (±3)	D57 (±3)	D1 (±3)	D14 (-3)	D1 (±3)						
Scans of the Chest, Abdomen and Pelvis		Day 1 of Cycles 2, 4, 6, 9, 13, 17, and Every 4th Cycle Thereafter (Window: Day -7 to Day 1 of Each Cycle)											be done, but the same method must be used throughout the study. A scan will be performed at the EoT if one was not performed within 30 days of the EoT Visit.		

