8.3. Adverse Event Management

8.3.1. Definition of an Adverse Event

An AE is defined as any untoward medical occurrence in a subject administered a medicinal product that does not necessarily have a causal relationship with this treatment. An AE can, therefore, be any unfavorable and unintended sign (including an abnormal laboratory finding), symptom, or disease temporally associated with the use of a medicinal (investigational) product, whether or not related to the study (investigational) product. This includes an exacerbation of pre-existing conditions or events, concurrent illnesses, drug interaction, or the significant worsening of the indication under investigation. Anticipated fluctuations of pre-existing conditions, including the disease under study that does not represent a clinically significant exacerbation or worsening, need not be considered AEs.

Symptoms of the disease under study/lack of efficacy/disease progression should not be classified as an AE if they are within the normal day-to-day fluctuation or expected progression of the disease.

It is the responsibility of the Investigator to document all AEs that occur during the study. AEs should be reported on the appropriate CRF.

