8.3.3. Reporting of Adverse Events and Serious Adverse Events

The AE reporting period begins from the time that the subject signs the ICF through and including 30 calendar days after the last study intervention dose. All subjects with treatment-related AEs/SAEs should be observed until resolution or stabilization. Any SAE occurring after the reporting period must be promptly reported if a causal relationship to the investigational drug is suspected. If the subject begins a new anticancer therapy, the safety reporting period ends at the time the new treatment is started, however, death must always be reported if it occurs during the AE reporting period irrespective of intervening treatment.

Elective or previously scheduled hospitalizations for pre-existing conditions that have not worsened after initiation of treatment should not be classified as SAEs. For example, an admission for a previously scheduled ventral hernia repair would not be classified as an SAE.

All AEs should be recorded individually unless, in the opinion of the Investigator or designated physician, the AEs constitute components of a recognized condition, disease, or syndrome. In the latter case, the condition, disease, or syndrome should be reported rather than each individual sign or symptom. If a constellation of signs and/or symptoms cannot be medically characterized as a single diagnosis or syndrome at the time of reporting, each individual event should be recorded as an AE or SAE as appropriate on the relevant form(s) (SAE Report Form and/or AE CRF). If a diagnosis is subsequently established, it should be reported as follow-up information becomes available. If a diagnosis is determined after the reporting of the constellation of symptoms, the signs/symptoms should be updated to reflect the diagnosis.

Each AE will be evaluated for duration, severity, seriousness, and causal relationship to the investigational drug. The action taken with study intervention and the outcome must also be recorded.

All SAEs, regardless of relationship to the study intervention, must be reported immediately (within 24 hours of awareness of event by Investigator) to the Sponsor and Contract Research Organization (CRO) pharmacovigilance group. Initial SAE notification should be made by e-mailing or faxing the SAE report form to the e-mail or fax number provided on the SAE report form.

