#### 4.3.1.2 Handling Missing Dates/Months/Years for Determination of TEAEs

Adverse events (AEs) with incomplete onset dates will be handled as follows for the purpose of determining treatment emergence according to the definition provided in [Section 4.11.2](#).

- If the start/end date of an AE is partially missing, the date will be compared as accurately as possible with the first dose of study drug and the date of last dose of study drug plus 30 days. The AE will be assumed to be treatment emergent if it cannot be definitively shown that the AE did not start or worsen during the treatment-emergent period.
- If the start date is completely missing, an AE will be considered treatment-emergent unless the stop date is before first dose of study drug.

The original partial or missing date will be displayed in the AE listings.

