#### 4.11.2 Adverse Events

Adverse events will be coded using Medical Dictionary for Regulatory Activities (MedDRA) Version 22 or higher. The severity grade of the AE will be assessed by the Investigator according to the National Cancer Institute Common Terminology Criteria for Adverse Events (NCI-CTCAE, Version 5.0). If an AE is not included in the NCI-CTCAE Version 5.0, the severity grade of the AE will be assessed by the Investigator according to the study protocol.

A treatment-emergent adverse event (TEAE) is defined as any AE that emerges or worsens in the period from the first dose of duvelisib to 30 days after the last dose of duvelisib. The onset date of an AE will be compared to the first dose date and the last dose date plus 30 days (inclusive) to determine whether the AE is treatment-emergent or not. Refer to [Section 4.3.1.2](#) for the algorithm to determine whether an AE is treatment emergent if the onset date of an AE is completely or partially missing.

TEAEs will be summarized for each treatment arm by MedDRA SOC and PT, or PT only, or SOC only. For summary tables by SOC and PT, SOC will be sorted alphabetically, and PT will be sorted by decreasing frequency in Arm 1 within each SOC. For summary tables by PT only, PT will be sorted by decreasing frequency. For selected summaries (indicated in the list below), TEAEs will be summarized by SOC, high-level group term (HLGT) and PT, sorted by most frequently occurring SOC.

If multiple TEAEs of the same PT are reported for a subject, only the maximum grade observed for this PT will be included in summary of TEAEs by grade; the subject will be counted only once in the number of subjects for this PT and only once for the number of subjects for the SOC to which the PT is classified.

An overview TEAE summary table will be provided which will include the number of subjects with AEs in selected categories. In addition, TEAEs will be summarized for the following categories, and will be tabulated by SOC and PT, unless otherwise specified.

- TEAEs (all grades, all causalities)
- Treatment-related TEAEs (all grades)
- TEAEs by maximum grade (all causalities)

- Treatment-related TEAEs by maximum grade
- Grade 3 or higher TEAEs (all causalities)
- Grade 3 or higher treatment-related TEAEs
- Treatment-emergent SAEs (all causalities)
- TEAEs resulting in discontinuation of study drug (all causalities)
- TEAEs resulting in dose hold (all causalities)
- TEAEs resulting in dose reduction (all causalities)

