#### 4.11.2.1 Other Adverse Events of Interest

Selected MedDRA PTs will be combined to create grouped PTs or categories to further characterize risks associated with duvelisib. The following risks will be summarized as Adverse Event of Special Interest:

- Diarrhea/colitis
- Infections
  - All infections, excluding Pneumonia and COVID-19 infections
  - Pneumonia
  - COVID-19 infections
- Cutaneous reactions
- Non-infectious pneumonitis
- Neutropenia
- Hepatotoxicity (as defined by transaminase elevations)

The specific PTs that will be combined for each risk are defined in [Appendix 1](#).

For each risk, PTs will be summarized at the grouped PT and individual PT (and grouped SOC if applicable), at the subject level:

- TEAEs (all grades, all causalities)
- Treatment-related TEAEs (all grades)
- Grade 1 or 2 only TEAEs (all causalities)
- Grade 3 or higher TEAEs (all causalities)
- Treatment-emergent SAEs (all causalities)
- TEAEs resulting in dose holds
- TEAEs resulting in dose reductions
- TEAEs resulting in dose holds or reductions
- TEAEs resulting in discontinuation of study drug (all causalities)
- Time to initial onset (defined as AE start date – first dose date + 1)

In addition, the following summaries will be created for each grouped PT within each grouped SOC, at the event level:

- Summary of dose modifications
  - Number of events resulting in dose holds
  - Number of events resulting in dose reductions
  - Number of events resulting in dose holds or reductions
  - Number of events resulting in discontinuation of study drug
- Summary of outcome
  - Number of events resolved
  - Number of events resolved with sequelae
  - Number of events resolved or resolved with sequelae
  - Number of events not resolved
- Duration of AE

- Concomitant medications used to treat AEs (a specific list of concomitant medications associated with each risk will be provided)

For each subject and each AE, the worst severity recorded will be attributed and used in the by-severity summaries. Similarly, the worst causality (most related to treatment) will be attributed and used in the by-causality summaries. If causality is missing, the worst case will be assumed (related to treatment).

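### SAP 4.11.2 counts worsening in its TEAE definition, but for complete dates it tests only the onset date, so a pre-dose AE that worsens on duvelisib and is kept as one record would be missed

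*SAP*

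**What the plan says.** **Definition.** SAP 4.11.2 defines a TEAE as "any AE that emerges or worsens in the period from the first dose of duvelisib to 30 days after the last dose of duvelisib". Both a new event and a worsened one qualify.

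**Test for complete dates.** The next sentence of SAP 4.11.2 gives the comparison that decides the matter: "The onset date of an AE will be compared to the first dose date and the last dose date plus 30 days (inclusive". It mentions neither a grade at first dose nor a date of worsening.

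**Test for incomplete dates.** SAP 4.3.1.2 has a different rule for partial dates: "The AE will be assumed to be treatment emergent if it cannot be definitively shown that the AE did not start or worsen" in the treatment-emergent period. Where no start date exists: "If the start date is completely missing, an AE will be considered treatment-emergent unless the stop date is before first dose of study drug".

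**Collection.** Protocol 8.3.3 says: "The AE reporting period begins from the time that the subject signs the ICF". The screening column in Protocol 1.3 is headed "Screening D-30 to D-1".

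**Recording of a worsening.** Protocol 8.3.1 says of its AE definition: "This includes an exacerbation of pre-existing conditions or events". SAP 4.11.2.1 says: "For each subject and each AE, the worst severity recorded will be attributed and used in the by-severity summaries". Neither document says whether a grade increase in an ongoing AE updates the existing record or opens a new one with its own onset date.

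**The concern.** The SAP states a definition with two limbs and then, for fully dated events, a test that can apply only one of them. This is a conflict between a rule and its own definition rather than a missing detail. It also makes the handling of an event depend on how well it is dated: worsening counts if the date is partial and is not examined if the date is complete.

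What is at stake is the safety description. Safety and tolerability of the drug holidays is a secondary objective, and Protocol 2.1 asks whether the schedules give acceptable or improved tolerability. Most of the AE summaries in SAP 4.11.2 and the subject-level summaries of special-interest events in SAP 4.11.2.1 are restricted to TEAEs. An event wrongly classed as non-TEAE leaves these tables, and the onset-only test cannot add an event in its place.

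**Working it through.** The documents state no figure on this point, so the check is to apply the written rules to one event.

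**Test event (illustrative).** Grade 1 diarrhea starts 10 days before first dose, after consent. It becomes Grade 3 on treatment Day 40, and drug is held. Under the definition in SAP 4.11.2 it worsened between first dose and 30 days after last dose, so it is a TEAE.

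**Outcome under the operating rules:**

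1. *Complete pre-dose onset date, one record carrying the worst grade.* Onset is before first dose, so the comparison in SAP 4.11.2 fails. **Not a TEAE**, against the definition.
2. *Worsening entered as a new AE dated Day 40.* Onset lies in the window. **TEAE**, as the definition requires.
3. *Partial start date, one record.* SAP 4.3.1.2 asks whether a start or a worsening in the period can be ruled out. It cannot. **TEAE**.
4. *Start date completely missing, one record.* The event did not stop before first dose. **TEAE**.

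Only case 1 departs from the definition. Cases 1 and 3 can be the same clinical event and differ only in the completeness of the date.

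**Knock-on for time to onset.** SAP 4.11.2.1 computes time to initial onset as AE start date − first dose date + 1. With the original start date this is −10 + 1 = −9 days. With the date of worsening, 39 days after first dose, it is 39 + 1 = 40 days. Bringing such events into the TEAE set therefore also requires a rule on which date to use.

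**Where a case 1 event is lost and where it survives:**

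- Lost: the TEAE tables in SAP 4.11.2 (among them Grade 3 or higher, SAE, dose hold and discontinuation) and the subject-level TEAE summaries of special-interest events in SAP 4.11.2.1.
- Kept: the listings of all AEs and all SAEs (SAP 4.11.2 to 4.11.3).
- Kept, for laboratory parameters: the table of worsening in CTCAE grade from baseline (SAP 4.11.4). It does not cover diarrhea/colitis, rash, infection or pneumonitis, and it does not carry seriousness or causality.
- Kept as exposure data: unplanned dose holds, dose reductions and discontinuations (SAP 4.11.1), which have no TEAE filter but are not tied to the AE.

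**Size.** The number of affected subjects cannot be derived. What can be stated is the effect per subject: with the planned 51 per arm, one subject missing from a table cell changes that cell by 1/51 = 2.0 percentage points, provided the subject has no other TEAE counted in the same cell.

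**The case against.** The strongest reply is that the loss depends on a recording convention that the documents do not give. The eCRF cited in SAP 1, or its completion guidance, may require a new record for each worsening. Protocol 8.3.1 treats an exacerbation as an AE in itself, and Protocol 8.2.1.1 has a clinically significant examination finding reported as an AE if it worsens after consent. If every worsening is a new entry, the onset test implements the definition correctly. This stands, and it makes the consequence conditional. It does not remove the mismatch, because neither passage requires a new record when the grade of an ongoing AE rises.

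A reader might infer more than the documents support:

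- *That every such AE drops out of every TEAE table.* This follows only in case 1. The worst-severity sentence in SAP 4.11.2.1 does not establish a single record: it fits several records of different grades equally well, and SAP 4.11.2 expects several TEAEs of one preferred term in a subject.
- *That the abnormal baselines allowed by eligibility (ANC from 1.0 × 10⁹/L, ALT/AST up to 3 × ULN) make the exposed group large.* Protocol 8.3.6 keeps laboratory abnormalities that are not clinically significant out of the AE record, and Protocol 8.2.1.1 sends significant examination findings present at screening to medical history. A later worsening would then be a first AE record with on-treatment onset, which the test captures. The exposed group is AEs that arise after consent, are ongoing at first dose and then worsen.
- *That a special-interest rate is understated by some fixed share.* Losing one of five subjects among 51 would move 9.8% (5/51) to 7.8% (4/51), but nothing in the documents supports the five or places the lost subject in that cell.

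It is also fair to say that no safety hypothesis is tested, that no formal comparison of arms is planned (Protocol 9.4.1), and that the same rule applies to both arms. This limits the consequence to descriptive counts. Those counts are nevertheless how the tolerability of each schedule will be described.

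**Conclusion.** The point holds in conditional form. SAP 4.11.2 contradicts its own definition for fully dated AEs, and SAP 4.3.1.2 shows that worsening was meant to count. If a worsening is kept on the original record with its pre-dose onset date, the event is classed as non-TEAE and left out of the TEAE tables while staying in the listings. If each worsening is entered as a new AE, nothing is lost and only the wording needs attention. The size cannot be calculated because both the recording convention and the frequency are absent; the direction, if the loss occurs, is toward fewer TEAEs. The documents do not show that events have been or will be lost. The correction is worth making because it is cheap and only brings the test into line with the stated definition.

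**What to change.** Replace the onset comparison in SAP 4.11.2 with: *An AE is treatment-emergent if its onset is from first dose to last dose + 30 days, or if its onset is before first dose and its CTCAE grade or seriousness increases within that period.* Add that the date of worsening is used for time to onset of such AEs.

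If the eCRF already enters each worsening as a new AE with its own onset date, the grade test is unnecessary. The SAP then needs only to state that convention. One of the two is enough, and neither calls for a change to CRF guidance.

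Cost: one SAP sentence and a check of AEs with pre-dose onset, which would also show whether the grade at first dose and the date of worsening are available for them. TEAE counts may rise slightly.

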4.2. Scientific Rationale for Study Design

Dosing with duvelisib 25 mg BID has been shown to be efficacious in multiple Phase 1-3 studies including subjects with iNHL. Data from the pivotal Phase 3 CLL/SLL study (DUO) and Phase 2 FL study (DYNAMO) showed that most tumor responses occurred by the end of Cycle 4 of duvelisib 25 mg BID treatment, and the majority of DIs for toxicity occurred primarily after 4 cycles. The post-hoc analysis of the DUO study showed that response to duvelisib was improved or maintained in most subjects who had ≥ 1 DI for > 1 week (84%) or > 2 weeks (82%), then followed by ≥ 3 weeks on duvelisib. PFS was also similar between subjects with ≥ 1 DI and those without DI for > 1 week or > 2 weeks within the first 3 months of therapy (median PFS: > 1 week, 17.8 vs 16.3 months; > 2 weeks, 17.8 vs 16.3 months) ([Flinn 2019](#)). These data support the hypothesis that prespecified 2-week drug holidays used in this study would not impact efficacy. Based on these results, the VS-0145-229 study will examine the effects of prespecified 2-week dose holidays on tumor responses (i.e., is uninterrupted dosing required in early cycles to

achieve responses, or can comparable tumor responses be achieved starting with alternating 2-week periods of dosing and holidays?) and safety/tolerability (i.e., will the holidays reduce the frequency, severity, and/or duration of AEs, allowing subjects to stay on treatment longer?).

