### 4.2 General Presentation Considerations

Baseline is defined as the last available pre-treatment assessment (scheduled or unscheduled). 'Treatment Day' will be calculated relative to the date of randomization, i.e., Treatment Day = Assessment Date - First Dose Date + 1.

The following visit windows will be defined for the purposes of determination of ORR per Lugano and revised IWG criteria at 6, 12, 18 and 24 months:

Timepoint	Visit Window
Month 6	155 – 211 (183 ± 28 days) from first dose
Month 12	351 - 407 days (379 ± 28 days) from first dose
Month 18	463 – 519 days (491± 28 days) from first dose
Month 24	687 – 743 days (715 ± 28 days) from first dose

For other by-visit summaries, data will be categorized based on the scheduled visit (i.e. cycle) specified on the eCRF on which the data were collected.

Continuous data will be summarized in terms of the mean, standard deviation (SD), median, minimum, maximum and number of observations, unless otherwise stated. Continuous data that are expected to be skewed will be presented in terms of the maximum, upper quartile, median, lower quartile, minimum and number of observations. The minimum and maximum will be reported to the same number of decimal places as the raw data recorded in the database. The mean, median, lower quartile and upper quartile will be reported to one more decimal place than the raw data recorded in the database. The SD will be reported to two more decimal places than the raw data recorded in the database. In general, the maximum number of decimal places reported shall be four for any summary statistic.

Categorical data will be summarized in terms of the number of subjects providing data at the relevant time point (n), frequency counts and percentages. Any planned collapsing of categories will be detailed in the SAP text and the data displays.

Percentages will be presented to one decimal place. Percentages will not be presented for zero counts. Percentages will be calculated using n as the denominator. If sample sizes are small, the data displays will show the percentages, but any textual report will describe frequencies only.

Changes from baseline in categorical data will be summarized using shift tables where appropriate.

P-values greater than or equal to 0.001, in general, will be presented to three decimal places. P-values less than 0.001 will be presented as “<0.001”.

Confidence intervals (CIs) will be presented to one more decimal place than the raw data.

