### 4.11.1 Extent of Exposure

Extent of exposure will be summarized for each treatment arm based on the AT analysis set. Extent of exposure will be summarized for the following variables:

- Duration (months): (date of last dose – date of first dose + 1) divided by (365.25/12).
- Number of cycles started (continuous and categorical)
- Relative dose intensity (overall and by cycle), defined as  $100\% \times (\text{total dose received})/(\text{planned cumulative dose for the duration of treatment})$ . The planned cumulative dose for the treatment duration is defined as 25 mg BID  $\times$  total number of days on which duvelisib is scheduled to be administered during the interval between first dose date and last dose date. The treatment scheme is provided in [Section 3.1](#).
- Number and percentage of subjects with a dose reduction
- Time from first dose to first dose reduction

- Total days spent at dose reduction: last date of dose reduction – first date of dose reduction + 1
- Number and percentage of subjects with an unplanned dose hold (excluding the planned 2-week holidays for each arm)
- Number and percentage of subjects with an unplanned dose hold < 7 days,  $\geq$  7 days
- Time from first dose to first unplanned dose reduction
- Number and percentage of subjects for whom study drug was discontinued

A by-subject listing will be presented for exposure to study drug

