- TEAEs resulting in dose hold or reduction (all causalities)
- TEAEs resulting in any dose modification (dose hold, dose reduction and/or discontinuation)
- TEAEs occurring during the first 10 weeks of treatment
- Treatment-related TEAEs resulting in discontinuation of study drug
- TEAEs by resolution status (resolved/resolved with sequelae vs. not resolved)
- Grade 3 and or higher TEAEs by resolution status (resolved/resolved with sequelae vs. not resolved)
- Treatment-emergent SAEs by resolution status (resolved/resolved with sequelae vs. not resolved)
- TEAEs resulting in death (all causalities)
- Treatment-related TEAEs resulting in death
- TEAEs reported in  $\geq 20\%$  of all treated subjects by PT (all grades, all causalities)
- Grade 3 or higher treatment-emergent AEs reported in  $\geq 20\%$  of all treated subjects by PT (all causalities)
- Treatment-emergent SAEs reported in  $\geq 2\%$  of all treated subjects by PT (all causalities)
- TEAEs reported in  $\geq 5\%$  of subjects and occurred at  $\geq 2\%$  higher incidence in subjects on Arm 1 (all grades, all causalities)
- Grade 3 or higher TEAEs reported in  $\geq 5\%$  of subjects on either arm (all causalities)

A by-subject listing of the following AE categories will be presented.

- All AEs (TEAEs will be flagged)
- All SAEs (TEAEs will be flagged)
- All SAE reported with the term disease progression
- TEAEs resulting in dose hold
- TEAEs resulting in dose reduction
- TEAEs resulting in discontinuation of study drug
- TEAEs resulting in death (see [Section 4.11.3](#) for full characterization of deaths)
- TEAEs resolved or resolved with sequelae
- TEAEs not resolved

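### Apart from one 10-week table, AE incidence is a crude subject count over a window that grows with time on treatment, so a true fall in AE rate can be hidden or reversed.

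*SAP*

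**What the plan says.** Protocol 4.2 poses the tolerability question: "will the holidays reduce the frequency, severity, and/or duration of AEs, allowing subjects to stay on treatment longer". It links AE frequency and time on treatment.

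SAP 4.11.2 sets the TEAE window: "any AE that emerges or worsens in the period from the first dose of duvelisib to 30 days after the last dose of duvelisib". Its overview is a count of subjects: "An overview TEAE summary table will be provided which will include the number of subjects with AEs in selected categories". In the tables by grade, each subject counts once per preferred term and once per system organ class. SAP 4.2 sets the denominator: "Percentages will be calculated using n as the denominator", where n is a number of subjects.

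Four other provisions bear on the point:

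- **Fixed window.** SAP 4.11.2 lists "TEAEs occurring during the first 10 weeks of treatment". SAP 4.11.2.1 lists no such table for AESIs.
- **Contrast between arms.** SAP 4.11.2 also lists TEAEs in at least 5% of subjects with at least 2% "higher incidence in subjects on Arm 1 (all grades, all causalities").
- **AESI timing.** SAP 4.11.2.1 lists "Time to initial onset (defined as AE start date" minus first dose date plus 1), AE duration, and event-level counts of outcomes and dose modifications.
- **Exposure.** SAP 4.11.1: "Extent of exposure will be summarized for each treatment arm based on the AT analysis set". These tables are separate from the AE tables.

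Neither document specifies a person-time rate or a censored cumulative incidence for any AE.

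**The concern.** A count of subjects with at least one event rises with the length of observation even when the underlying rate is constant. Here the observation window follows time on treatment, and time on treatment is itself something the schedules are meant to improve. A schedule that is better tolerated, and so kept up for longer, gives its subjects more time in which to have a first event.

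The full-period tables therefore mix two things that Protocol 4.2 asks about separately: how often AEs occur, and how long subjects stay on drug. At stake is the descriptive answer to the tolerability question. The primary ORR analysis is not affected.

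**Working it through.** **Inputs from the documents.** The window and denominator are as above. Follow-up runs to 2 years after the last randomization (SAP 3.1), so I cap exposure at T = 24 months. The arms differ only in Cycle 1: 10 × 7 = 70 scheduled dosing days in Arm 1 and 6 × 7 = 42 in Arm 2. Ten weeks is 70 / (365.25/12) = 2.30 months.

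**Inputs assumed.** The plan has no AE rate or treatment duration to reproduce. I take constant AE hazards of 2 to 10 per 100 subject-months, hazard ratios (HR) of 0.6 to 1.0, and mean time on treatment of 6 vs 9, 6 vs 12 or 9 vs 12 months. The 30-day tail is ignored.

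**Step 1: equal hazard, fixed exposure.** Crude incidence = 1 − exp(−hazard × months).

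| Hazard per month | 6 months | 9 months | Gap (points) |
|---|---|---|---|
| 0.03 | 16.5% | 23.7% | 7.2 |
| 0.06 | 30.2% | 41.7% | 11.5 |
| 0.10 | 45.1% | 59.3% | 14.2 |

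The rate is the same in each row, so the whole gap comes from exposure.

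**Step 2: lower hazard, longer treatment.** Let time on treatment be exponential with discontinuation hazard m = 1/mean, and let L be the AE hazard. Crude incidence = L/(L+m) × [1 − exp(−(L+m)T)]. Time at risk per subject = [1 − exp(−(L+m)T)]/(L+m).

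- Reference schedule, L = 0.05, mean 6 months: 0.05/0.21667 × (1 − exp(−5.2)) = 22.9%, about 12 of 51. Time at risk is 4.59 months.
- Better-tolerated schedule, L = 0.04, mean 12 months: 0.04/0.12333 × (1 − exp(−2.96)) = 30.8%, about 16 of 51. Time at risk is 7.69 months.

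The crude order is wrong. Crude incidence divided by time at risk returns 5.0 and 4.0 per 100 subject-months, the right order.

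**Step 3: when the order reverses.** With reference L = 0.05:

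| HR | 6 vs 9 months | 6 vs 12 months | 9 vs 12 months |
|---|---|---|---|
| 0.8 | 22.9% vs 25.8% | 22.9% vs 30.8% | 30.4% vs 30.8% |
| 0.7 | 22.9% vs 23.2% | 22.9% vs 27.8% | 30.4% vs 27.8% |
| 0.6 | 22.9% vs 20.5% | 22.9% vs 24.7% | 30.4% vs 24.7% |

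Over hazards of 2 to 10 per 100 subject-months, reversal needs an HR above about 0.68–0.70 (6 vs 9), 0.53–0.56 (6 vs 12) or 0.77–0.80 (9 vs 12).

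**Step 4: the planned 10-week table.** The same formula with T = 2.30 gives 9.1% vs 8.0% for the Step 2 example, the right order. At equal hazard (5 per 100 subject-months, 6 vs 12 months) it gives 9.1% vs 9.9%, against 22.9% vs 36.0% over the full period. This table is little affected by exposure, but it stops at week 10. Protocol 4.2 says most toxicity interruptions in the earlier studies came after 4 cycles. Four cycles here end at week 22 (10 + 4 + 4 + 4).

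**The case against.** The plan is not confined to whole-period counts. The 10-week table covers the only stretch in which the two schedules differ; afterwards both arms dose in Weeks 3 and 4 of each cycle. The Protocol 4.2 remark on late interruptions describes earlier 25 mg BID studies, not these schedules. AE duration and time to onset are planned for AESIs. Time to treatment failure (TTF), with 6- and 12-month estimates, measures persistence directly. Exposure is tabulated by arm, so an imbalance would be visible. Both arms have holidays, and no formal comparison is planned. Protocol 9.4.4 leaves room for further analyses of toxicity rates.

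Much of this stands. It limits the problem mainly to AEs after week 10 and to AESIs, and it means exposure may diverge little between the arms.

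It does not remove the problem. Exposure tables show an imbalance without adjusting incidence for it. Time to onset has no censoring rule, so as written it covers only subjects who had the event. Event-level counts have no person-time denominator. Protocol 9.4.4 is permissive and names no method. The Arm 1 table is itself a crude contrast between arms, and it would not list an excess on Arm 2. The pooled monotherapy percentages in Protocol 2.3.1, such as 49.0% for diarrhea/colitis, invite the same crude comparison with earlier duvelisib experience.

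A reader might go further and infer that the better-tolerated schedule will show more AEs, or that the safety objective cannot be assessed. The documents support neither. Reversal depends on hazard and exposure ratios that they do not give, and they do not predict which arm would stay on treatment longer. Incidence over actual treatment also remains a valid description of each arm.

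**Conclusion.** The point holds as a gap in prespecification: outside the 10-week TEAE table, no planned incidence summary separates AE rate from time on treatment. The full-period tables can mislead if exposure differs between arms or from continuous dosing.

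Whether they do depends on the data. Under the assumptions above, equal rates can look 7 to 14 points apart at 6 versus 9 months. A 20% rate reduction reverses in all three exposure scenarios, though only marginally at 9 versus 12 months. A 40% reduction reverses only at 6 versus 12 months. These figures rest on constant hazards and assumed treatment durations; events that cluster early would weaken the effect. This is an inexpensive improvement to a descriptive safety analysis, not an error that invalidates it.

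**What to change.** Keep the crude tables. In SAP 4.11.2 and 4.11.2.1 add, by arm, for each AESI, Grade 3 or higher TEAEs, SAEs and TEAEs leading to discontinuation:

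1. **First-event incidence per 100 subject-months with 95% CI.** Time at risk runs from first dose to the earliest of first event, last dose + 30 days, death, start of new anticancer therapy, or data cutoff. Planned holidays count as time at risk. Report overall and split into 0–10 weeks and later.
2. **Cumulative incidence at 6 and 12 months.** Treat death, and the end of the TEAE risk period for any reason other than data cutoff, as competing events. Treat data cutoff as censoring.

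State that AE frequency by schedule is read from the rates, alongside the cumulative incidence and TTF. The rates are needed because cumulative incidence with discontinuation as a competing event still reflects time on treatment. In the Step 2 example the same formula gives 16.8% vs 17.0% at T = 6 and 21.4% vs 25.0% at T = 12. It shows absolute risk at a fixed time, not the rate.

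The cost is some extra tables from AE and dosing dates already collected. The rates assume a roughly constant hazard within each period, which the 10-week split eases but does not remove.
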